6.3.2.2 Eliciting and Documenting Adverse Events

The investigator is responsible for reporting AEs that are observed or reported during the study, regardless of their relationship to study drug or their clinical significance. Serious AEs will be collected from the time that the patient gives consent to participate in the study until 30 days after the date of last dosing or of completion or withdrawal from the study, whichever is latest. All AEs will be collected starting from the time that the patient gives consent until the date of completion or withdrawal from the study.

Serious AEs that occur more than 30 days after the last dose of study drug or after exit from the study, whichever is later, need not be reported unless the investigator considers them related to study drug.

At each study visit, patients will be asked a standard non-leading question to elicit any medically related changes in their well-being. They will also be asked if they have been hospitalised, had any accidents, had any eye surgery, used any new medications, or changed concomitant medication regimens (both prescription and over-the-counter medications).

In addition to patient observations, AEs identified from any study data (eg, laboratory values, physical examination findings) or identified from review of other documents that are relevant to patient safety will be documented on the AE page in the eCRF.

6.3.2.3 Reporting Adverse Events

All AEs reported or observed will be recorded on the AE page of the eCRF. Information to be collected includes event term, time of onset, date of resolution of the event, seriousness, severity, relatedness to study drug, any required treatment or evaluations, and outcome.

The investigator will assess the severity of the event. The severity (intensity) of AEs must be classified using the following criteria:

- **Mild:** An AE that is easily tolerated by the patient, causes minimal discomfort, and does not interfere with everyday activities
- **Moderate:** An AE that causes enough discomfort to interfere with normal everyday activities and may require intervention
- **Severe:** An AE that prevents normal everyday activities (treatment or intervention will usually be required). Severe events are usually incapacitating

When changes in the severity of an AE occur more frequently than once a day, the maximum intensity for the event must be noted for that day. Any changes in intensity of signs and symptoms over multiple days will be captured by recording new AEs, with the amended intensity grades and the dates (and time, if known) of the change(s). Changes in the intensity

of an AE must be documented to allow an assessment of the duration of the event at each level of intensity.

The investigator will assess the causal relationship between the study medication and the AE and decide whether, in his or her qualified medical judgement, there is a reasonable possibility that the event may have been caused by the study drug. There are 2 categories of causality:

- **Unrelated:** If no valid reason exists for suggesting a relationship, or the event may plausibly be related to the patient's clinical condition, an underlying disease or other medication taken by the patient, then the AE must be considered unrelated.
- **Related:** If there is any valid reason for supposing that there is a relationship between the study medicine and the AE, especially if the event improves on withdrawal of the drug (de-challenge) or recurs on recommencement of therapy (re-challenge), then the AE must be considered related. The AE must not be considered related simply because it is not possible to rule out an association between the AE and the study drug.

The investigator's assessment of an AE's relationship to study drug is part of the documentation process, but it is not a factor in determining what is or is not reported in the study. If there is any doubt as to whether a clinical observation is an AE, the event must be reported.

The action taken with the study medication must be recorded as treatment continued, treatment interrupted, or treatment discontinued. If the patient is no longer taking study medication at the time of the event, then action taken must be recorded as not applicable.

All AEs will be followed to adequate resolution. The Medical Dictionary for Regulatory Activities (MedDRA) will be used to code all AEs.

Any AE that meets SAE criteria (Section 6.3.2.1) must be reported to the [REDACTED] Pharmacovigilance Department immediately (ie, within 24 hours) after the time site staff first learn about the event, using the electronic data capture (EDC) system. If for any reason the EDC is not available to the study site, the following contact information is to be used for SAE reporting:

██████████ **Pharmacovigilance Department**

If the initial contact to ██████████ Pharmacovigilance is made via the SAE Hotline or the SAE fax line, the SAE must still be reported, urgently, using the EDC system when it becomes available. Details on SAE reporting are presented in the study manual.

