Merely repeating an abnormal test, in the absence of any of the above conditions, does not require reporting as an AE. An abnormal test result that is determined to be an error or artefact does not require reporting as an AE.

A treatment-emergent AE (TEAE) is defined as any event not present before exposure to study drug or any event already present that worsens in either intensity or frequency after exposure to study drug.

An SAE is defined as any event that

- results in death.
Any death resulting from an AE occurring during the study period or within 30 days after the last dose of the study drug, even if the death appears to be completely unrelated to the study or study drug.

- is immediately life threatening.
The term ‘life-threatening’ refers to an event in which the patient was at risk of death at the time of the event; it does not refer to an event that hypothetically might have caused death if it were more severe.
- requires inpatient hospitalisation or prolongation of existing hospitalisation.
The term ‘hospitalisation’ means a hospital admission or an overnight stay; prolongation means delay of a planned or anticipated discharge date by at least 1 overnight stay. Adverse events which require attendance at hospital but do not require admission may be considered medically important.
- results in persistent or significant disability/incapacity.
- results in impairment, damage, or disruption in the study patient’s body function or structure, or physical ability or quality of life.
- is a congenital anomaly/birth defect.
Additionally, events in which there is suspicion that exposure of either parent to the study drug resulted in an adverse outcome in the offspring is a medically important event.
- Is medically important: an event that may not be immediately life-threatening or fatal or result in hospitalisation, but may require intervention to prevent one of the serious outcomes listed above.
Examples of such events are intensive treatment in an emergency room or at home for allergic bronchospasm; blood dyscrasias; convulsions that do not result in hospitalisation; or development of drug dependency or drug abuse.

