7.7.4.1 Adverse Events

All AEs will be listed and all TEAEs will be summarised. Adverse events will be deemed treatment-emergent if the onset date is on or after the date of first treatment. Events which are not treatment-emergent will be listed separately and together with all other AEs. AEs will be summarised separately for the treatment period, the tapering phase, and the 9-month follow-up period. Ocular TEAEs will be summarised separately from non-ocular TEAEs. Ocular TEAEs will be summarised separately for the study eye and non-study eye.

Treatment-emergent AEs will be summarised by treatment group, presenting the number and percentage of patients having a TEAE in each system organ class and having each individual TEAE based on the preferred term. Treatment-emergent AEs will also be tabulated according to intensity and causality. Patients who experienced multiple TEAEs for a preferred term will be counted once, similarly for patients with multiple TEAEs per system organ class.

Deaths, SAEs, and TEAEs leading to discontinuation of study treatment will be listed separately and, if appropriate, summarised by treatment group, system organ class and preferred term.

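### Recording each change in AE intensity as a new AE, with treatment-emergence judged by onset date alone, turns an improving pre-dose surgical event into a TEAE, contrary to the protocol's own definition

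*Protocol*

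**What the plan says.** Four parts of the protocol bear on this.

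- **Recording (Section 6.3.2.3).** Under this rule, a shift in grade that plays out over several days "will be captured by recording new AEs, with the amended intensity grades and the dates". It is not limited to worsening. Its stated purpose is that each shift in the grade "of an AE must be documented to allow an assessment of the duration of the event at each level of intensity". The items to be collected for each AE do not include a link from a new record to the event it continues.
- **Collection window (Section 6.3.2.2).** "All AEs will be collected starting from the time that the patient gives consent until the date of completion or withdrawal from the study". Collection therefore starts before surgery (Visit 2, Day -1) and before the first dose (Visit 3, Day 1). Table 6-1 schedules AE documentation at Visit 2.
- **Definition of a TEAE (Section 6.3.2.1).** Apart from events not present before exposure, a TEAE is "any event already present that worsens in either intensity or frequency after exposure to study drug".
- **Analysis (Section 7.7.4.1).** "Adverse events will be deemed treatment-emergent if the onset date is on or after the date of first treatment". No worsening condition appears there. Further, "AEs will be summarised separately for the treatment period, the tapering phase, and the 9-month follow-up period", and "Patients who experienced multiple TEAEs for a preferred term will be counted once, similarly for patients with multiple TEAEs per system organ class".

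Section 7.7 leaves methods and data conventions to the SAP. The SAP document supplied is an addendum to primary SAP v2.0 and contains no AE analyses.

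**The concern.** Taken one at a time, the rules are ordinary. Together they let improvement count as onset. Every randomised patient has surgery the day before the first dose, so the boundary between pre-dose and post-dose falls inside the immediate post-operative course. An event first recorded on Day -1 at one grade and on a later day at a lower grade gives a second AE record dated after the first dose. Under Section 7.7.4.1 that record is treatment-emergent; under Section 6.3.2.1 the event is not. Once the step-down is a separate, unlinked record, nothing in it shows that the event was already present, so the analysis cannot apply the Section 6.3.2.1 definition without reconstructing the link.

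The same mechanism can repeat one event across the three period summaries.

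Safety and tolerability is a secondary objective, safety has no hypothesis testing (Section 7.7.4), and there is no safety or data monitoring committee (Sections 6.4 and 11.1.1). The descriptive TEAE tables therefore carry much of the safety comparison, and TEAEs are also tabulated by intensity with no stated maximum-grade rule.

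**Working it through.** The plan gives no figure to reproduce. The check traces its rules through example event histories.

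**Inputs from the protocol:** surgery on Day -1 (Section 5.8.1); first dose on Day 1 (Section 5.2); a new record at each multi-day grade change (Section 6.3.2.3); TEAE if onset is on or after first treatment (Section 7.7.4.1); TEAE only if new or worse after exposure (Section 6.3.2.1); 20 patients per arm (Section 7.4).

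**Assumptions:** the event dates below are invented for illustration. Week 12 is taken as Day 84 and the end of the two-week taper as Day 98 (84 + 14). Records are assigned to a period by their onset date.

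| Event history | AE records | TEAE records by onset date (7.7.4.1) | Period summaries the patient enters | TEAEs by whole event (6.3.2.1) |
|---|---|---|---|---|
| Severe Day -1, moderate Day 5, resolved | 2 | 1 | treatment | 0 |
| Severe Day -1, moderate Day 5, mild Day 90, resolved | 3 | 2 | treatment, taper | 0 |
| Severe Day 20, moderate Day 90, mild Day 120 | 3 | 3 | treatment, taper, follow-up | 1 |
| Starts Day -1, no grade change | 1 | 0 | none | 0 |

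**What the counting rule repairs.** Counting a patient once per preferred term removes repeats inside one table. It does nothing in the first row: the patient should contribute 0 and contributes 1. In the third row it is not stated to reach across the separate period summaries.

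**When nothing goes wrong.** The last row shows that an event which resolves without an intermediate grade creates no new record. A mild pre-dose event cannot step down, so it cannot be misclassified this way. A repeat in the taper or follow-up needs a grade change dated in that period.

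**Scale.** If the safety set has 20 patients in an arm, and the patient has no other TEAE with the same preferred term, the added incidence is 100 × k / 20 percentage points for k misclassified patients:

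- k = 1: 5 points
- k = 2: 10 points
- k = 4: 20 points

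The documents give no value for k.

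**The case against.** The strongest reply has four parts.

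**Section 6.3.2.1 already excludes the example.** A Day -1 event that only improves is neither new nor worse. Section 6.3.2.3 still speaks of one event with a duration at each intensity, so the onset date in Section 7.7.4.1 could be read as the onset of the whole event. This stands in part: the documents do not say which section prevails, and it would be wrong to claim that Section 7.7.4.1 plainly overrides the definition. But its wording is date-only, and with unlinked records the more generous reading cannot be applied from the data alone.

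**Primary SAP v2.0 may settle it.** TEAE derivation, period assignment and collapsing of records could all be there. This stands as a limit on the conclusion. The conflict inside the protocol remains either way.

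**The cross-period repeat is conditional.** The rule that assigns an AE to a period is not stated, nothing says the period tables will be added together, and a patient still symptomatic in the taper is not plainly out of place in a taper table. Table 6-1 has no visit between Weeks 12 and 16, so a grade change dated in the taper would usually be reported in retrospect. This stands. The repeat is possible, not certain.

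**Consequences are contained.** All AEs are listed, so parent events can be traced, and the affected tables are descriptive. This also stands, and it limits the severity.

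A reader might go further and infer that surgical background would swamp a true K-321 excess. Let b be the share of patients with a pre-dose AE that steps down after dosing, and let p1 and p0 be the other TEAE rates on K-321 and placebo, independent of b. The observed difference is [b + (1 − b)p1] − [b + (1 − b)p0] = (1 − b)(p1 − p0). An assumed 20-point excess becomes 10 points at b = 50% and 2 at b = 90%. The documents do not support choosing high values of b. It requires that an AE is recorded before the first dose, that it is moderate or severe, and that it steps down rather than resolving directly. If each is assumed to have a 50% chance, b = 0.5³ = 12.5% and the excess is 17.5 points; at 80% each, b = 0.8³ = 51.2% and it is 9.8 points. The formula also describes only an any-TEAE row. For a single preferred term, dilution arises only where that same term was a pre-dose event in the patient.

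**Conclusion.** The point holds in limited form. Applied as written, Sections 6.3.2.3 and 7.7.4.1 give a TEAE for a pre-dose surgical AE that only improves, and this contradicts Section 6.3.2.1. Counting once per preferred term does not cure it. A step-down dated in the taper or follow-up can also appear as a new AE of that period, on the unstated assumption that records are placed by onset date.

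The size is unknown. Each misclassified patient moves a term's incidence by 5 percentage points in an arm of 20. How many there would be depends on how often pre-dose AEs are recorded and regraded, which the documents do not give. They therefore do not support any particular loss of a drug difference, or a conclusion that the safety comparison is invalid. The primary endpoint is untouched. The conclusion also assumes that primary SAP v2.0 does not already collapse linked records. With that reserve the change should be made, because stated rules produce a count that the protocol's own definition rejects.

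**What to change.** First confirm whether primary SAP v2.0 already links or collapses intensity records. If it does, Section 7.7.4.1 needs only to be brought into line with Section 6.3.2.1. If it does not:

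1. Link every intensity-change record to its parent event, by an eCRF field or, if the eCRF cannot change, by a programming step with documented matching rules.
2. In Section 7.7.4.1, derive treatment-emergence and study period from the parent event's onset. Count a later record as a new TEAE only if the event worsens after the first dose, as Section 6.3.2.1 requires. Name the grade against which worsening is judged, and the period to which a worsening belongs.
3. State explicitly how AEs are assigned to the treatment, taper and follow-up summaries.
4. In the table by intensity, use the maximum post-dose grade once per event.
5. Keep the dated intensity records, so that duration at each grade can still be reported.

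The cost is protocol and SAP wording plus one link field or some programming. No extra visits or assessments are needed. If the link has to be made in programming, some matches will need review, which is manageable at about 60 patients.

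### The two mandatory causality definitions overlap, so an adverse event with both a drug link and a plausible alternative cause must be coded both ways

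*Protocol*

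**What the plan says.** Protocol section 6.3.2.3 gives the investigator four instructions on causality.

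- **Standard.** The investigator decides, on medical judgement, whether "there is a reasonable possibility that the event may have been caused by the study drug".
- **Number of categories.** "There are 2 categories of causality": unrelated and related. There is no intermediate category.
- **Unrelated.** This code is compulsory on either of two grounds. The first is that no valid reason for a link exists. The second is that the event may plausibly stem from the patient's clinical condition, "an underlying disease or other medication taken by the patient, then the AE must be considered unrelated".
- **Related.** The definition opens "If there is any valid reason for supposing that there is a relationship between the study medicine and the AE" and makes that code compulsory. Positive de-challenge and re-challenge are named as particular support. One limit follows: "The AE must not be considered related simply because it is not possible to rule out an association".

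The code is used later. Section 7.7.4.1 states: "Treatment-emergent AEs will also be tabulated according to intensity and causality". Under section 6.3.2.2, serious events after the collection window "need not be reported unless the investigator considers them related to study drug". Section 6.3.2.4 deals with suspected unexpected serious adverse reactions. It describes the sponsor's assessment of expectedness but does not say whose causality judgement makes an event a suspected reaction.

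**The concern.** The second ground for the unrelated code needs only a plausible alternative. It does not ask whether the drug is also a plausible cause. The related definition needs only a valid reason to suspect the drug, and makes no exception for alternative causes. Both are compulsory, so an investigator who sees both explanations cannot obey the text.

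In this trial that situation is likely to be common for the study eye. Fuchs dystrophy is an entry requirement (section 4.1.1), descemetorhexis is done on Day -1, and other post-operative drops are recommended by default (section 5.8.1). A red or oedematous eye soon after surgery could reasonably prompt both explanations.

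What is at stake is the meaning of the causality code. If investigators settle the overlap differently, the related counts reflect local reading habits as well as the drug. The wording also leans one way: the related definition carries an explicit brake, and the unrelated definition has no matching one.

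**Working it through.** No sample-size, power or error-rate calculation applies, and the plan states no figure to reproduce. The check is to run the definitions through the possible cases.

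| Case | Unrelated definition | Related definition | Reasonable-possibility standard |
|---|---|---|---|
| (a) No valid reason for a drug link | Met (first ground) | Not met | Unrelated |
| (b) Valid reason, no plausible alternative | Not met | Met | Related |
| (c) Valid reason and a plausible alternative | Met (second ground) | Met | Related, if the drug remains a reasonable possibility |

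Cases (a) and (b) are determined. Case (c) meets both compulsory definitions, and nothing in section 6.3.2.3 says which prevails. The standard would usually point to related, because a second plausible cause does not remove a reasonable possibility of the first. The second ground for unrelated says the opposite, so it conflicts with the standard as well as with the related definition.

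**How many events are affected.** Let k be the number of events in an arm that fall in case (c). The number of these coded related can be anything from 0 (unrelated always prevails) to k (related always prevails). The documents give no event rates and no frequency of alternative explanations, so k cannot be calculated.

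**Spread across sites.** Section 4.1 plans about 60 patients at about 30 sites: 60 / 30 = 2 patients per site on average. A site with two patients can hold at most two of the three arms, so differences in reading between sites cannot cancel within such a site. They add noise to a small table.

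**Where the code matters.**

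- The table of treatment-emergent events by causality (section 7.7.4.1): directly affected.
- Identification of suspected reactions (section 6.3.2.4): affected by inference only.
- Late serious events (section 6.3.2.2): the restriction begins at the later of study exit and 30 days after the last dose. A completer stops dosing at about Week 14 and exits at Week 52, so it begins about 52 - 14 = 38 weeks after the last drop. The effect for completers is marginal. It begins sooner for early withdrawals.

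**Where it does not matter.** Section 6.3.2.3 says that relatedness does not decide what is reported during the study, and every serious event goes to pharmacovigilance within 24 hours. Section 7.7.4.1 lists all adverse events and summarises all treatment-emergent events by arm, with ocular events shown separately for the study eye. None of that uses the causality code.

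**The case against.** The strongest reply is that the text already supplies what is needed. The lead-in leaves the decision to qualified medical judgement on a reasonable-possibility standard, and the related definition covers any event with a valid drug link. The most informative safety comparison is the masked, randomised comparison of all treatment-emergent events with placebo. Every arm has the same disease and surgery, so that comparison needs no causality code.

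Much of this stands. It rules out several stronger readings that a reader might infer:

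- *That almost no study-eye event can be coded related.* The related definition permits that code and, on its own terms, requires it. The code is undetermined, not forced to unrelated.
- *That an event recurring on re-challenge must be called unrelated.* The related definition names re-challenge as particular support. A recurrence may also make the alternative less plausible.
- *That expedited reporting is largely switched off.* Serious events during the study reach pharmacovigilance whatever their code, and section 6.3.2.4 does not say that the site's code alone decides what is suspected. The absence of a safety committee or external data monitoring committee (sections 6.4 and 11.1.1) does not change that flow.
- *That a specific undercount can be stated.* Any such figure would rest on assumed event rates and on unrelated always prevailing, which the text does not establish.

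There are also limits on how wide the overlap is. Surgery is not named in the unrelated definition, so counting its effects depends on reading them into the patient's clinical condition. The post-operative agents and their schedule are redacted, so how long they could explain an event is unknown.

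The reply does not remove the contradiction. Medical judgement cannot satisfy two compulsory and opposite instructions. The SAP addendum contains no rule to settle the matter. The primary SAP is not among the documents reviewed.

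**Conclusion.** The point holds as a contradiction in a stated rule. An adverse event with both a valid reason for a drug link and a plausible alternative cause meets both compulsory definitions, without precedence, and the unrelated definition departs from the protocol's own standard.

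That many study-eye events with a suspected drug link would fall in the overlap is a judgement. It rests on the universal disease, the universal surgery and the default post-operative drops, and its size cannot be calculated. The consequence is confined to the causality table, by inference the classification of suspected reactions, and marginally late serious events. Safety is descriptive only (section 7.7.4), and neither the efficacy analyses nor the all-causality summaries by arm depend on this code. It should be corrected, but the trial's validity does not turn on it.

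**What to change.** In section 6.3.2.3, delete the second ground for the unrelated code and make the two categories exclusive on the existing standard:

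- **Related:** there is a reasonable possibility, supported by a valid reason, that study drug caused or contributed to the event, even if another cause is also plausible.
- **Unrelated:** there is no such reasonable possibility.

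Keep the sentence that failure to rule out an association is not enough on its own. It prevents the revised definition from sweeping in every event. A separate eCRF item for the alternative cause (disease, surgery, other drops) would be useful but is optional.

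The change should precede causality coding. The SAP addendum refers to an unmasking after Week 12, so any later recoding should be done only by assessors who are still masked.

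The cost is one paragraph of protocol wording and a note to sites, plus one eCRF field if the optional item is taken up. The downside is small: somewhat more events would be coded related. Dosing, schedule, sample size and the efficacy analyses do not change.
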